2.2 Overall Study Design

This prospective, Phase III, multicentre, randomised, open-label, parallel group, active-controlled study will compare triptorelin pamoate PR 3-month with triptorelin acetate PR 1-month for the treatment of Chinese female subjects with endometriosis.

Subjects with endometriosis will be screened for eligibility up to 5 weeks prior to the first dose of investigational medicinal product (IMP), which must occur during the follicular phase of the menstrual cycle. A total of 300 eligible subjects will be stratified by endometriotic surgical history (previous vs. no previous surgery) and the severity of endometriosis-associated pelvic pain (assessed by a visual analogue scale (VAS): VAS >3 or ≤ 3 cm) and randomised in a 1:1 ratio to receive either triptorelin pamoate PR 3-

Statistical Analysis Plan

Version: Final 3.1

Ipsen Pharma; Protocol No. D-CN-52014-220

Date of Issue: 13DEC2019

CCI

[figure not shown]
month once per 12 weeks (total 2 injections, one each at baseline and Week 12) or triptorelin acetate PR 1-month once per 4 weeks (total 6 injections, one each at baseline and Week 4, 8, 12, 16 and 20) for a 24-week treatment phase.

All subjects will visit the study site every 4 weeks until Week 24. The subgroup participating in the full PK and exploratory PD evaluations (up to 32 subjects, 16 from each treatment group, enrolled at the selected site) will have additional study visits during the treatment phase. If needed in the opinion of investigator, “add back” treatment (recommended as, but not limited to, tibolone at a dose of 2.5 mg once daily) may be applied from Week 12. After 24 weeks’ study treatment, subjects receiving triptorelin pamoate PR 3-month and participating in the full PK/PD subgroup will visit the study site, and other subjects will be followed up by telephone every 4 weeks until menses recovery or Week 40 (whichever is earlier). All subjects will attend the study site for the end of study visit (the first visit after menses recovery, or Week 40).

This study will consist of a screening period of up to 5 weeks, a 24-week open-label treatment period and a follow up period of up to 16 weeks. The duration of the study is a minimum of 24 to 40 weeks, plus up to 5 weeks for the screening period.

The principal study design features are summarised in Figure 1. The scheduled events at every visit are summarised in Table 5 (all subjects) and Table 6 (PK/PD subgroup subjects).

Figure 1 Study Design

[a] additional visits for subjects in the PK/PD subgroups not indicated

[b] during follow up, the first visit after menses recovery, or Week 40 (whichever is earlier) is considered the end of study visit

2.3 Sample Size and Power

The sample size was estimated based on data from Ipsen Study E-28-52014-705. Assuming the percentage of subjects castrated at Week 12 of triptorelin acetate PR 1-month treatment is no less than 92%, a sample size of 133 subjects in each treatment group will have 85% power to demonstrate the noninferiority of

Statistical Analysis Plan

Version: Final 3.1

Ipsen Pharma; Protocol No. D-CN-52014-220

Date of Issue: 13DEC2019

CCI

triptorelin pamoate PR 3-month to the comparator, when the lower limit of the 95% confidence interval (CI) of the difference in percentage of subjects castrated at Week 12 between the treatment groups is $\geq -10\%$ and with a 0.025 one-sided type I error rate.

Assuming that the dropout rate will be around 10%, a sample size of 300 randomised subjects in total is planned for this study.

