10.2 Sample Size Determination

Sample size was estimated based on data from Ipsen Study E-28-52014-705.[5] Assuming the percentage of subjects castrated at Week 12 of triptorelin acetate PR 1-month treatment is no less than 92%, a sample size of 133 subjects in each treatment group will have 85% power to

demonstrate the noninferiority of triptorelin pamoate PR 3-month to the comparator, when the lower limit of the 95% confidence interval (CI) of the difference in percentage of subjects castrated at Week 12 between the treatment groups is $>-10\%$ and with a 0.025 one-sided type I error rate.

Assuming that the dropout rate will be around 10%, a sample size of 300 randomised subjects in total is planned for this study.

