7.6 Efficacy

7.6.1 Primary Efficacy Analysis

The primary efficacy analysis is to compare the percentage of subjects castrated ($E_2 \leq 184$ pmol/L or 50 pg/mL) at Week 12 in triptorelin pamoate PR 3-month and triptorelin acetate PR 1-month groups on the PP subjects using as-treated assignments.

The null hypothesis for the primary efficacy analysis is that triptorelin pamoate PR 3-month is inferior to triptorelin acetate PR 1-month. The alternative hypothesis is that triptorelin pamoate PR 3-month is noninferior to triptorelin acetate PR 1-month, where the pre-specified non-inferiority margin is -10%:

$$H_0: P_{3\text{-month}} - P_{1\text{-month}} \leq -10\%$$

$$H_a: P_{3\text{-month}} - P_{1\text{-month}} > -10\%$$

Where $P_{3\text{-month}}$ denotes the percentage of subjects ($E_2 \leq 184$ pmol/L or 50 pg/mL) for triptorelin pamoate PR 3-month at Week 12, $P_{1\text{-month}}$ denotes the percentage of subjects ($E_2 \leq 184$ pmol/L or 50 pg/mL) for triptorelin acetate PR 1-month at Week 12.

The number and percentage of subjects castrated ($E_2 \leq 184$ pmol/L or 50 pg/mL), and its 95% asymptotic CI will be summarised for each treatment group at Week 12. The difference in percentage of subjects castrated (triptorelin pamoate PR 3-month – triptorelin acetate PR 1-month) and the 2-sided 95% CI of the difference will also be presented and calculated using the Miettinen and Nurminen method, stratified by randomisation stratification factors (endometriotic surgical history and the severity of endometriosis-associated pelvic pain at baseline) with sample size weighting⁵. In a case where the stratification factor recorded in the eCRF and IWRS are inconsistent, the eCRF data will be retained included as the randomization stratification factors as the covariates. If the lower limit of the 95% CI for the difference is $> -10\%$, triptorelin pamoate PR 3-month non-inferiority to triptorelin acetate PR 1-month will be confirmed.

The sensitivity analysis will be performed on the same analyses adding centre in the above Miettinen and Nurminen method.

The difference in percentage and its 2-sided 95% CI are also calculated using the Miettinen and Nurminen method without stratification factors for support analyses.

The primary efficacy analyses will be repeated for the FAS subjects using as-randomised assignments.

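### The 85% power stated for 133 per group fits a Wald-type formula; the Miettinen-Nurminen interval that decides non-inferiority has about 81%

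*SAP*

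**What the plan says.** SAP 2.3 gives the sizing assumptions. The control rate: "Assuming the percentage of subjects castrated at Week 12 of triptorelin acetate PR 1-month treatment is no less than 92" percent. The result: "a sample size of 133 subjects in each treatment group will have 85% power to demonstrate the noninferiority of" the 3-month product. The error rate: "with a 0.025 one-sided type I error rate". Protocol 10.2 says the same: "a sample size of 133 subjects in each treatment group will have 85% power to" show non-inferiority. The protocol synopsis repeats the statement. None of these places names the sample-size formula or gives the rate assumed for the 3-month arm.

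On enrolment, SAP 2.3 says: "Assuming that the dropout rate will be around 10%, a sample size of 300 randomised subjects in total is planned for this study".

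The decision rule is in SAP 7.6.1. The confidence interval for the difference is "calculated using the Miettinen and Nurminen method, stratified by randomisation stratification factors", with sample-size weights, and non-inferiority is concluded if its lower limit lies above the margin. Protocol 10.3 and 10.4.6.1 specify a two-sided 95% interval without naming a method, so Miettinen-Nurminen appears only in the SAP. The SAP does not recompute power for that method.

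**The concern.** A power figure belongs to a particular test. A Wald-type calculation uses the variance at the assumed true rates (92% and 92%). The Miettinen-Nurminen interval is a score interval: at the margin it uses the variance of the rates that best fit the data while differing by exactly 10 points, here about 85% and 95%. That variance is larger, so the same data clear the margin less often.

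If the 85% came from the first method and the trial uses the second, the planning figure describes a test that will not be run. The chance of missing non-inferiority when the two formulations are equally effective at 92% would be understated.

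**Working it through.** **Inputs**
- Control rate 92%, stated as a floor (SAP 2.3, Protocol 10.2).
- 3-month rate: not stated. I assume 92%, the value that reproduces 133; other values are run below.
- Margin: SAP 7.6.1, "where the pre-specified non-inferiority margin is -10" percentage points.
- One-sided alpha 0.025, so z = 1.960. Target power 85%, so z = 1.036.
- Allocation: "randomised in a 1:1 ratio to receive either triptorelin pamoate PR 3"-month or the 1-month product (SAP 2.2).

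**Step 1: reproduce the plan's figure (Wald-type normal formula)**

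n = (1.960 + 1.036)² × 2 × 0.92 × 0.08 / 0.10² = 132.2, rounded up to 133.

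Standard error at 133 = √(2 × 0.92 × 0.08 / 133) = 0.03327.

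Power = Φ(0.10 / 0.03327 − 1.960) = 85.2%. Exact binomial power of the Wald interval is 85.5%.

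Both stated figures are recovered. Because the two rates are equal, pooled and unpooled variances coincide, so the contrast that matters is Wald against score.

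**Step 2: the score formula with the same inputs**

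Constrained to a -10 point difference, the fitted rates are 84.8% (3-month) and 94.8% (1-month). The variance terms are 0.1291 and 0.0495, against 0.0736 each at 92%.

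Standard error under the constraint = √((0.1291 + 0.0495) / 133) = 0.03665.

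Power = Φ((0.10 − 1.960 × 0.03665) / 0.03327) = about 80%.

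This formula would need 151 per arm for 85%, so it is not the source of 133.

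**Step 3: exact power of the Miettinen-Nurminen rule**

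All 134 × 134 outcomes were enumerated at 133 per arm. Success was counted when the lower 95% limit, including the N/(N−1) variance factor, exceeded -10 points.

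| Evaluable per arm | True rates (3-month / 1-month) | Power |
|---|---|---|
| 133 | 92% / 92% | 81.4% |
| 135 | 92% / 92% | 82.6% |
| 144 | 92% / 92% | 85.2% |
| 146 | 92% / 92% | 84.8% |
| 147 | 92% / 92% | 86.0% |
| 150 | 92% / 92% | 85.9% |
| 133 | 92.5% / 92% | 85.9% |
| 133 | 93% / 92% | 89.8% |
| 133 | 93% / 93% | 85.0% |
| 133 | 94% / 94% | 88.6% |
| 133 | 97% / 94% | 99.7% |

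The row for 135 is the planned 300 less 10%: 150 × 0.90 = 135. The last row uses the rates that Protocol 1.3 reports from the earlier European study. Power moves in small steps because the outcomes are discrete: it first reaches 85% at 144 per arm and stays at or above it from 147.

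**Step 4: does stratification change this?**

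The stratified, sample-size-weighted version was simulated (100,000 trials each) for several assumed stratum splits, with 92% in every stratum. Power was 81.2% to 81.6% at 133 per arm and about 82.0% to 82.5% at 135. The documents do not give the expected stratum sizes, so the splits are assumptions, but the result hardly depends on them.

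**Step 5: type I error**

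At the null boundary (82% against 92%, 133 per arm) the Miettinen-Nurminen rule rejects 2.39% of the time and the Wald rule 2.93%. Part of Wald's apparent power therefore comes from exceeding 2.5%.

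**The case against.** The arithmetic is hard to dispute, so the case against rests on framing and consequence.

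- **The source is inferred.** No formula is named. This stands: the fair statement is that a Wald-type formula reproduces 133 and 85%, while the score formula does not.
- **The 3-month rate is not stated.** Half a point in favour of the 3-month arm (92.5% against 92%) brings power to 85.9%. This also stands, and it is a reason to state the assumption. Equal rates are what reproduce the plan's own number.
- **92% is a floor.** At 93% in both arms power is 85.0%, and at the earlier study's rates it is 99.7%. True, but a claim of 85% power when the rate is no less than 92% has to hold at 92%, and there it does not.
- **The protocol names no interval method.** So its figure contradicts nothing else in the protocol. That does not help the SAP, which repeats the 85% and also specifies the score interval.
- **Little follows in practice.** Power stays above 80% at the planning rate, the conclusion will rest on the observed interval, and SAP Final 3.1 comes late in the study. This limits the remedy to a correction of the text. It does not make the stated figure right.

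**Conclusion.** The concern holds. With 92% in both arms, a margin of -10 points and one-sided 0.025, the planned analysis has about 81% power at 133 evaluable per arm and about 83% at 135. Against the stated 85%, the shortfall at 133 is about 4 points, and type II error is 18.6% where the plan implies 15%.

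The result rests on equal true rates at the 92% floor, and on 133 to 135 subjects per arm reaching the primary analysis. SAP 5.5 makes the per-protocol set primary and requires a Week 12 measurement and no major deviation affecting the endpoint, so the evaluable number could fall below 135. Higher true rates would remove the shortfall. The analysis method is sound and holds its type I error; the power statement is what needs correcting.

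**What to change.** In the protocol synopsis, Protocol 10.2 and SAP 2.3, replace the power statement with one that matches the analysis: with 133 evaluable subjects per arm and a true castration rate of 92% in both arms, the Miettinen-Nurminen analysis has about 81% power at a margin of -10 points and one-sided 0.025, and about 83% with 135 per arm. Say explicitly that the 3-month rate is assumed equal to the 1-month rate. A note that power at 133 per arm is about 85% at 93% in both arms would give useful context.

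The cost is two sentences, repeated where the figure appears, and a slightly less favourable headline number. Enrolment, margin, interval method and decision rule stay as they are. For scale only: holding 85% at the 92% floor would take about 147 evaluable per arm, which at 10% dropout is 147 / 0.90 = 163.3, or 164 per arm and 328 randomised. That increase is not requested.

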3 EFFICACY AND SAFETY VARIABLES

3.1 Primary Efficacy Endpoint(s)

The percentage of subjects castrated ($E_2 \leq 184$ pmol/L or 50 pg/mL) at Week 12. The primary endpoint will be evaluated on centralised bioanalysis of serum samples for E_2 .

3.2 Secondary Efficacy Endpoints

The secondary endpoints for this study include:

- Percentage of subjects castrated ($E_2 \leq 184$ pmol/L or 50 pg/mL) at Weeks 4 and 8.
- Percentage of subjects castrated ($E_2 \leq 110$ pmol/L or 30 pg/mL) at Weeks 4, 8 and 12.
- Change in endometriosis-associated pelvic pain (by 10 cm VAS) at Weeks 4, 8 and 12 compared to baseline.
- E_2 , FSH and LH concentrations at Weeks 4, 8 and 12.
- Time to menses recovery.

3.3 Exploratory Efficacy Endpoints

The exploratory endpoints for this study include:

- Percentage of subjects castrated (as defined by both $E_2 \leq 184$ pmol/L (50 pg/mL) and $E_2 \leq 110$ pmol/L (30 pg/mL)) at Week 24.
- Change in endometriosis-associated pelvic pain (by 10cm VAS) at Weeks 16, 20 and 24 and the end of study visit compared to baseline.
- Concentrations of E_2 , FSH and LH at Week 24.
- The PK/PD relationship will be explored (PD markers: E_2 , FSH and LH) for triptorelin acetate PR 1-month formulation and triptorelin pamoate PR 3-month formulation.

3.4 Safety Variables

The safety and tolerability of triptorelin will be assessed by evaluating as follows:

- Adverse events (AEs) throughout the study,
- Clinical laboratory parameters (biochemistry, haematology and urinalysis) test results at screening, Weeks 12 and 24,
- Electrocardiogram (ECG) findings at screening, Weeks 12 and 24,
- Serum hormone (E_2 , FSH and LH) concentrations at Week 40 (for those subjects whose menses do not recover at Week 40),

Statistical Analysis Plan

Version: Final 3.1

Date of Issue: 13DEC2019

Ipsen Pharma; Protocol No. D-CN-52014-220

CCI

- Vital signs (blood pressure and heart rate) measurements at each visit during treatment and end of study visit,
- Physical/pelvic examination at screening, Weeks 12 and 24,
- Pelvic type B ultrasound at screening (or within 1 month prior to screening), Week 12 (optional) and Week 24,
- Urinary pregnancy test at screening and baseline visit.

4 PHARMACOKINETIC VARIABLES

A full triptorelin PK characterisation, using a non-compartmental analysis (NCA) approach, will be conducted in a subgroup of up to 16 subjects in each treatment group to be enrolled at selected sites. PK parameters (C_{min} , C_{max} , t_{max} and AUC_{tau} where applicable) will be calculated for triptorelin acetate PR-1 month after the first administration and triptorelin pamoate PR 3-month after the first and last administration.

5 ANALYSIS SETS

5.1 Screened Set

All subjects screened (i.e. who signed the informed consent) are included in Screened set.

5.2 Randomised Set

All subjects randomised (i.e. who were randomly allocated to a treatment group) are included in the Randomised Set.

Randomised subjects are analysed according to their assigned treatment.

5.3 Safety Set

The Safety Set includes all subjects who received at least one dose of study medication.

The Safety Set will be used for safety analyses according to the actual treatment received for each subject.

5.4 Full Analysis Set (FAS)

The full analysis set (FAS) includes all randomised subjects who received at least one dose of study medication with at least one baseline and at least one post-baseline assessment of the primary efficacy parameter.

The FAS will be used to analyse primary and secondary efficacy endpoints. All exploratory efficacy endpoints will be performed on the FAS.

FAS subjects are analysed according to their randomised treatment.

5.5 Per Protocol (PP) Set

The per protocol (PP) set includes all subjects in the FAS with primary endpoint measurement at week 12, and without major protocol violations/deviations affecting primary efficacy endpoint.

Major protocol deviations are those that affect the primary efficacy endpoint and the criteria of major protocol deviations will be defined in the file of protocol deviation document. The process to review major

Statistical Analysis Plan

Version: Final 3.1

Ipsen Pharma; Protocol No. D-CN-52014-220

Date of Issue: 13DEC2019

CCI

protocol deviations will be ongoing and the final PP subjects will be determined during the data review meeting held prior to database lock.

The PP set will be used to analyse primary and secondary efficacy endpoints.

The PP set will be the primary analysis population for the primary efficacy endpoint.

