10.1.1 Data Sets Analysed

Analysis of the primary and secondary efficacy endpoints will be performed on the FAS and the PP set. All exploratory efficacy analyses will be performed on the FAS. PK analyses will be performed on the full PK profile analysis set and the sparse PK sampling analysis set, as appropriate.

The analyses of safety data will be performed based on the safety set.

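### The SAP confirms non-inferiority on the PP set alone and gives the repeated FAS analysis no role in the decision, although the protocol names both sets and ranks neither

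*SAP*

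**What the plan says.** **Protocol.** Section 10.1.1 says "Analysis of the primary and secondary efficacy endpoints will be performed on the FAS and the PP set". It does not rank the two sets or say that both must pass. The decision rule in sections 10.3 and 10.4.6.1 (lower limit of the 95% CI above -10%) names no analysis set.

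**SAP.** Section 5.5 says "The PP set will be the primary analysis population for the primary efficacy endpoint". It limits that set to "all subjects in the FAS with primary endpoint measurement at week 12" and without a major deviation affecting the primary endpoint. Section 7.6.1 runs the primary test on PP, as treated, and treats non-inferiority as confirmed if the lower limit exceeds -10%. It then adds "The primary efficacy analyses will be repeated for the FAS subjects using as-randomised assignments". No text says what follows if the two results disagree, and section 8 lists no change to the planned analyses.

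**Related rules.** SAP 6.2 fills a missing E2 with the last post-baseline value. SAP 5.4 admits to the FAS only women with a baseline and a post-baseline E2. SAP 6.1 re-maps an early-withdrawal visit on Days 82-109 to Week 12, so a few women who withdraw around then can still enter PP.

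**The concern.** PP membership depends on events after randomisation: having a Week 12 sample and having no major deviation. Randomisation does not protect that comparison. Apart from the re-mapped visits, women who leave before Week 12 cannot affect the deciding result, whatever their last E2 showed. The carried-forward rule for E2 can change the Week 12 result only in the FAS, which is the set without a vote.

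The trial is open-label, and the Week 12 requirement for PP entered with SAP Final 3.1, dated 13 December 2019. In a non-inferiority trial the two sets can be biased in different directions, so agreement between them is what makes the claim credible. As written, a failing FAS result would be reported but could not stop the claim.

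**Working it through.** **Inputs.** Margin: SAP 7.6.1, "where the pre-specified non-inferiority margin is -10" percent. Error rate: Protocol 10.2, "with a 0.025 one-sided type I error rate". Planned size: "a sample size of 133 subjects in each treatment group will have 85% power". Comparator rate: "Assuming the percentage of subjects castrated at Week 12 of triptorelin acetate PR 1-month treatment is no less than 92" percent. Dropout around 10%, 300 randomised, 1:1. The test-arm rate is not stated; I take it as 92% too.

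**1. The plan's own figure.** n per arm = (z0.975 + z0.85)² × [p1(1-p1) + p2(1-p2)] / margin² = (1.960 + 1.036)² × (2 × 0.92 × 0.08) / 0.10² = 8.98 × 14.72 = 132.2, rounded up to 133. Power at 133 by this formula is 85.2%. For dropout, 266 / 0.9 = 296, close to the 300 planned. The figure reproduces.

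**2. Can PP pass where another reading of the same data fails?** Assume 150 per arm, 30 missing at Week 12 (10%), about 92% castrated among those measured, and no other exclusions. Limits are unstratified Miettinen-Nurminen; the SAP's primary interval is stratified.

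| Missing, 3-month vs 1-month | PP counts | PP lower limit | Missing as not castrated | Lower limit |
|---|---|---|---|---|
| 15 vs 15 | 124/135 vs 124/135 | -6.9 | 124/150 vs 124/150 | -8.7 |
| 18 vs 12 | 121/132 vs 127/138 | -7.3 | 121/150 vs 127/150 | -12.7 |
| 20 vs 10 | 120/130 vs 129/140 | -6.7 | 120/150 vs 129/150 | -14.6 |

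An even split passes both ways. At 18 vs 12 and at 20 vs 10, PP passes and missing-as-not-castrated fails.

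**3. What the SAP's own FAS would do at 18 vs 12.** Suppose all 30 women have a post-baseline E2, and all 12 missing comparator women carry a castrated value (127 + 12 = 139/150).
- All 18 test-arm women carry a castrated value: 121 + 18 = 139/150, lower limit -6.3; passes.
- 4 of the 18 carry a non-castrated value: 135/150, lower limit -9.4; passes.
- 5 of the 18 do: 134/150, lower limit -10.2; fails, while PP still passes at -7.3.

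So the FAS carries information that PP discards, but only as far as the last E2 shows it.

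**4. Cost in power.** Simulated trials, same interval method, equal missingness per arm, carried-forward values castrated at the arm's true rate.

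| Setting | PP alone | PP and carried-forward FAS | PP and missing-as-not-castrated |
|---|---|---|---|
| 92%/92%; 148 per arm, 7% missing, 2% violators | 82% | 80.5% | 64% |
| 92%/92%; 148 per arm, 10% missing, 2% violators | 81% | 79% | 58% |
| 92%/92%; 150 per arm, 10% missing | 82% | 81% | 59% |
| 97%/94%; 148 per arm, 7% missing, 2% violators | above 99% | above 99% | 93% |

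The 97% and 94% rates are those the protocol reports for the earlier European study (section 1.3).

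**The case against.** **The SAP does not contradict the protocol.** A reader might infer that the protocol requires success in both sets and that the SAP dropped this. The text does not support that. The protocol lists both sets, its rule names neither, and section 10.4 leaves analytical detail to the SAP. Naming PP as primary fills a gap, and the FAS result will be produced and reported. This stands. What remains is that nothing says what a discordant FAS does to the conclusion.

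**Adding the FAS does not cure the dropout problem.** In step 3 the carried-forward FAS passes whenever the dropouts' last values were mostly castrated. It also omits women with no post-baseline E2. This stands, and is why a separate sensitivity analysis is needed.

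**An extreme dropout pattern proves little.** One can assume that 10% of the 3-month arm are missing and all uncastrated, while 5% of the 1-month arm are missing and 92% castrated. PP then passes in about 82% of trials, and an analysis of true status in 4%. A reader might infer that PP hides a failure of that size. But true status of absent women cannot be observed. In the same scenario a carried-forward FAS with values castrated at 92% passes in 86%, and missing-as-not-castrated in about 25%. Nor do the documents support the pattern: before Week 12 only the 1-month arm has further injections due (Weeks 4 and 8), so only those women miss doses by leaving early. I do not rely on it.

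**Missing-as-not-castrated as a gate.** A reader might infer that this stricter version could be made a condition at similarly small cost. Step 4 shows that it could not.

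**Conclusion.** The point holds in limited form. The SAP allows non-inferiority to be confirmed on PP alone, a set conditioned on a Week 12 value, and a failing FAS cannot block it. The protocol neither prescribes nor rules this out. The gap can matter at the plan's own 10% missingness with a modest imbalance: at 18 vs 12, PP gives -7.3 and missing-as-not-castrated gives -12.7.

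This rests on assumed splits, equal 92% rates and unstratified intervals. It shows what could happen, not what did. The SAP should be changed because the remedy uses two analyses already planned and costs about 1.5 points of power at 92%/92%.

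**What to change.** 1. In SAP 5.5 and 7.6.1, state that non-inferiority is concluded only if the lower limit of the two-sided 95% CI exceeds -10% in both the PP set and the FAS as already defined, with carried-forward E2. Cost: wording, and power of about 80.5% instead of 82% at 92%/92%; above 99% at 97%/94%.
2. Add a sensitivity analysis on all randomised women that counts a missing Week 12 E2 as not castrated, or a tipping-point analysis. It uses data already collected.
3. State that the analysis in item 2 is not a condition for success. As a gate it would lower power to about 58-64% at 92%/92% with 7-10% missing per arm, in a trial planned at 85%.
4. Record the decision rule in SAP section 8, since the protocol states none for the case where the sets disagree.
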